6.4.3. Groups 1 and 2: Week 24 and 72 Assessments

Study Visit for Weeks 24 and 72 should be completed \pm 7 days of the protocol-specified visit date, based on the Baseline Visit. Group 2 subjects will follow local standard of care for renal monitoring. The following assessments and procedures will be performed and recorded on CRFs:

- Complete physical exam including vital signs, body weight and height
- Blood samples for:
 - Plasma HBV DNA (for PCR)
 - HBV serology (HBeAg and HBsAg; anti-HBe and anti-HBs (if HBsAg negative))
 - Hematology (CBC with differential and platelets, PT/INR)
 - Group 1: Serum renal chemistry (glucose, creatinine, creatinine clearance (calculated), magnesium, bicarbonate, chloride, potassium, sodium), fasting required
 - Liver chemistry (ALT, ALP, AST, total and direct bilirubin, total protein, albumin, GGT, LDH, CK), fasting required
 - Group 1 Only: Serum bone chemistry (calcium, phosphorus, 1,25 hydroxy vitamin D, PTH, osteocalcin, bone alkaline phosphatase, N and C telopeptides), fasting required
- Group 1 Only: DEXA (+/- 14 days of the Week 24 or Week 72 visit) scan of spine and whole body
- Group 1: Urinalysis (glucose, protein, creatinine, phosphate, bicarbonate, blood, calcium), fasting required
- Review of bone and renal AEs and any associated medical management
- Concomitant medications (including dietary supplements such as calcium, vitamin D, phosphorus)
- Assessment of medication adherence

- Tenofovir DF dispensing and instructions on appropriate dosing and administration
- Screening for pregnancy (urine screen)

Subjects who discontinue the study prior to the Week 24 or 72 Visit will complete all Week 24 or 72 assessments and procedures at an Early Drug Discontinuation Visit, to be completed within 72 hours of last dose of Tenofovir DF. Subjects who have received at least one dose of Tenofovir DF and permanently discontinue treatment will be followed for 24 weeks off treatment or up to initiation of an alternative treatment regimen, whichever occurs first.

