Baseline measures for Groups 1 and 2 will include laboratory assessments for HBV DNA, HBV serology, HCV, HDV, and HIV polymerase chain reaction (PCR) testing, HBV genotyping, serum renal and bone chemistries, liver function, hematology, urinalysis. Dual Energy X-ray Absorptiometry (DEXA) imaging and a physical exam, including current concomitant medications (including dietary supplements) and any renal or bone AEs, will also be collected.

FREQUENCY OF STUDY PROCEDURES ([Appendix 2](#)):

Subjects enrolled to either Group 1 or 2 will have the following measures assessed:

- HBV DNA: every 12 weeks from Baseline to Week 96
- HBV serology: every 24 weeks from Baseline to Week 96
- Liver chemistry (i.e., alanine aminotransferase (ALT), alkaline phosphatase (ALP), aspartate aminotransferase (AST), total and direct bilirubin, total protein, albumin, gamma glutamyl transpeptidase (GGT), lactate dehydrogenase (LDH), creatine kinase (CK): every 24 weeks from Baseline to Week 96
- Hematology (i.e., complete blood count with differential and platelets, PT/INR): every 24 weeks from Baseline to Week 96
- Physical Examination and Drug Dispensing: every 12 weeks from Baseline to Week 96

Subjects enrolled to Group 1 will have the following additional monitoring:

- DEXA: every 24 weeks from Baseline to Week 96 (5 scans)
- Serum bone chemistry (i.e., calcium, phosphorus, vitamin D levels (25-hydroxy and 1,25 dihydroxyvitamin), parathyroid hormone (PTH), osteocalcin, bone-specific alkaline phosphatase, N and C telopeptides): every 24 weeks from Baseline to Week 96
- Serum renal chemistry (i.e., glucose, creatinine, calculated creatinine clearance, magnesium, bicarbonate, chloride, potassium, sodium): at 4 weeks and 12 weeks from Baseline and every 12 weeks thereafter to Week 96, according to SmPC

- Urinalysis (i.e., protein, glucose, creatinine, phosphate, bicarbonate, blood, calcium): at 4 weeks and 12 weeks from Baseline and every 12 weeks thereafter to Week 96

Subjects enrolled to Group 2 will have the following monitoring:

- DEXA: every 48 weeks from Baseline to Week 96 (3 scans)
- Serum bone chemistry (i.e., calcium, phosphorus, vitamin D levels (25-hydroxy and 1,25 dihydroxyvitamin), PTH, osteocalcin, bone-specific alkaline phosphatase, N and C telopeptides): every 48 weeks from Baseline to Week 96
- Serum renal chemistry and urinalysis according local standards of care

Product, Dose, and
Mode of
Administration:

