Western and northern Europe are areas of low endemicity (< 2% prevalence), while some countries of Eastern Europe are areas of high endemicity (> 8% prevalence) {19056}. In areas with high endemicity, such as Asia and sub-Saharan Africa, CHB infections are usually the result of perinatal (vertical) or child-to-child (horizontal) transmission. The mode of transmission has clinical implications because 90% of children infected in the first year of life and 30% to 50% of children infected between ages 1 and 4 years develop CHB.

Despite the availability of HBV vaccine programs in many countries, new HBV infections are still common, including areas of low endemicity such as the United States (US) and Europe {26406}. In Europe, 13.34 million people are chronically infected with HBV, with an estimated 36,000 deaths from HBV related causes annually {24854}, {25143}. Among 28 reporting EU countries, over 17,000 cases of HBV were reported in 2011; with over two-thirds of cases being newly identified CHB {26854}, {26858}. Challenges with reporting acute and chronic HBV cases mean that calculations of burden are very likely underestimated. CHB infection is the primary source of HBV-related morbidity and mortality, with up to 25% of early deaths associated with HBV cirrhosis or liver cancer {26858}. Those with CHB infection have a 12 to 300 times greater risk of hepatocellular carcinoma (HCC) than non-carriers {26858}.

There is a paucity of aggregated incidence data on HBV in children in Europe, partly due to the difficulty in identifying cases, as affected children are often virtually asymptomatic while Hepatitis B surface antigen (HBsAg) or Hepatitis B e (core) antigen (HBeAg) positive. A seroprevalence study conducted in 2007 within the Netherlands demonstrated an overall prevalence of 0.5% (95% CI 0.2-1.1) among children 0 to 14 years, and among indigenous children, the prevalence is only 0.1% (95% CI 0-1.0). The overall prevalence of HBV in the Netherlands is estimated at 3.5% {26855}. In a recent cross-sectional study among a large sample of UK schoolchildren aged 7 to 11 years old, 0.26% (95% CI 0.14-0.44) had persistent acute, or resolved HBV infection {26851}. Unlike infection during adulthood, children often exhibit immune tolerance during their initial infection with HBV, with only a very small proportion of children clearing HBsAg and either exhibiting HBeAg loss or seroconversion {27079}

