Following acute hepatitis B infection, up to 90% of children become chronic carriers of the virus. Hepatitis B virus infection in children is usually asymptomatic, with a low rate of disease progression during the first 2 decades of life. There are four characteristic immunologic phases to this disease. In the first phase, the immune tolerant phase, patients have high HBV DNA levels and have detectable HBsAg and HBeAg. The hallmark of this phase is a normal ALT. The second phase that follows, known as the immune active stage, is characterized by persistently elevated ALT levels, an indicator of liver damage, even though children may show no signs or symptoms of disease. The third phase, the inactive HBsAg carrier stage, is characterized by undetectable or low levels of HBV DNA and the presence of anti-HBe antibodies. This third stage can evolve into a fourth stage, reactivation, in which ALT levels are abnormal and HBV DNA levels are increased.

The management of CHB in children and adolescents is still evolving {17786}. Current consensus is that no treatment is indicated in the immune tolerant (phase 1) or the inactive carrier state (phase 3). For children and adolescents in stages 2 or 4; however, treatment may be warranted in order to suppress viral replication and to prevent the emergence of complications, such as cirrhosis, decompensated liver disease, and HCC. Among infants and young children infected with HBV, 15-25% will die prematurely from these conditions {2826}. Although histological abnormalities are usually less severe in children than in adults, HBV infected infants and children are at higher risk for the eventual development of cirrhosis and primary HCC. In HBeAg-positive patients, treatment can lead to HBeAg loss and, more rarely, anti-HBe seroconversion, with the goal of subsequent HBsAg loss and seroconversion to anti-HBs. Achieving durable viral suppression in CHB infection usually requires long-term therapy, preferably utilizing potent oral regimens that limit the development of resistance.

1.2. Medicinal Product Name:

300mg Tenofovir disoproxil fumarate, Tenofovir DF (Viread®), which is equivalent to 245mg Tenofovir disoproxil.

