6.4.6. Groups 1 and 2: Week 96 Assessments/End of Treatment Visit

The Study Visit for Week 96/End of Treatment should be completed \pm 7 days of the protocol-specified visit date, based on the Baseline Visit. The following assessments and procedures will be performed and recorded on CRFs:

- Complete physical exam including vital signs, body weight and height
- Blood samples for:
 - Plasma HBV DNA (for PCR)
 - HBV serology (HBeAg and HBsAg; anti-HBe and anti-HBs (if Ag negative))
 - Hematology (CBC with differential and platelets, total and direct bilirubin, total protein, albumin, GGT, PT/INR)
 - Serum renal chemistry (glucose, creatinine, creatinine clearance (calculated), magnesium, bicarbonate, chloride, potassium, sodium), fasting required
 - Liver chemistry (ALT, ALP, AST, total and direct bilirubin, total protein, albumin, GGT, LDH, CK), fasting required
 - Serum bone chemistry (calcium, phosphorus, 1,25 hydroxy vitamin D, PTH, osteocalcin, bone alkaline phosphatase, N and C telopeptides), fasting required
- Urinalysis (glucose, protein, creatinine, phosphate, bicarbonate, blood, calcium), fasting required
- Groups 1 and 2: DEXA scan (+/- 14 days of the Week 96 visit) of spine and whole body
- Review of bone and renal AEs and any associated medical management
- Concomitant medications (including dietary supplements such as calcium, vitamin D, phosphorus)
- Assessment of medication adherence
- Tenofovir DF accountability
- Screening for pregnancy (urine screen)

Subjects who discontinue the study prior to the Week 96 Visit will complete all Week 96 assessments and procedures at an Early Drug Discontinuation Visit, to be completed within 72 hours of last dose of Tenofovir DF. Subsequent off-study therapy, if any, is at the discretion of the subject/physician and will not be provided by Gilead Sciences. Subjects who have received at least one dose of Tenofovir DF and permanently discontinue Tenofovir DF treatment will be followed for 24 weeks off treatment or up to initiation of standard of care treatment, whichever occurs first.

The study treatment will end after the each subject reaches Week 96.

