Appendix 2. Study Procedures Table

Study Procedures	Study Week												
	Screening	Baseline	4	12	24	36	48	60	72	84	96	30d Follow-Up	
Written Informed Consent	x												
Medical History	x												
HBV DNA		x		x	x	x	x	x	x	x	x		
HBV serology	x	x			x		x		x		x		
HCV, HDV, HIV testing		x											
HBV genotype		x											
DEXA, Group 1		x			x		x		x			x	
DEXA, Group 2		x					x					x	
Serum bone chemistry, Group 1		x			x		x		x			x	
Serum bone chemistry, Group 2		x					x					x	
Serum renal chemistry, Group 1	x	x	x	x	x	x	x	x	x	x	x	x	
Serum renal chemistry, Group 2*	x	x										x	
Liver chemistry	x	x			x		x		x			x	
Hematology		x			x		x		x			x	
Urinalysis, Group 1 (see * for Group 2)	x	x	x	x	x	x	x	x	x	x	x	x	
Complete physical examination	x	x		x	x	x	x	x	x	x	x	x	
Changes in medical status or symptoms, Group 1 (see † for Group 2)		x	x										
Drug dispensed and accountability/Concomitant medications		x	x	x	x	x	x	x	x	x	x	x	
Assess for AE, including renal and bone events (see † for Group 2)		x	x	x	x	x	x	x	x	x	x	x	x
Pregnancy test	x	x		x	x	x	x	x	x	x	x	x	

[figure not shown]
* Group 2 will follow local standard of care for renal monitoring, which may include the Tenofovir DF SmPC recommended screening intervals

† Group 2 subjects may have changes in medical status or symptoms and new AE assessed upon return for renal monitoring, as per standard of care and within the 12 week intervals of scheduled physical examinations

Definitions:

HBV serology	HBeAg, HBsAg, anti-Hbe, anti-HBs
Serum bone chemistry	calcium, phosphorus, 25-hydroxy and 1, 25 dihydroxyvitamin, PTH, osteocalcin, bone alkaline phosphatase, N and C telopeptides
Serum renal chemistry	glucose, creatinine, creatinine clearance (calculated), magnesium, bicarbonate, chloride, potassium, sodium
Liver chemistry	alanine aminotransferase (ALT), alkaline aminophosphatase (ALP), aspartate aminotransferase (AST), total and direct bilirubin, total protein, albumin, gamma glutamyl transpeptide (GGT), LDH, CK
Hematology	PT/INR, complete blood count (CBC) with differential, platelets
Urinalysis	glucose, protein, creatinine, phosphate, bicarbonate, blood, calcium
Complete physical exam	includes vital signs, body weight and height

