3.8.3. Selection of Data in the Event of Multiple Records in a Window

Depending on the statistical analysis method, single values may be required for each analysis window. For example, change from baseline by visit usually requires a single value, whereas a time-to-event analysis would not require one value per analysis window. When a single value is needed, the following rule(s) will be used:

Serology

In the event that 2 or more serology results (eg, HBeAg and anti-HBe or HBsAg and anti-HBs) occur within the same visit window, then the pair will remain together and the last pair of results in the window will be used for analysis purposes.

ALT

The highest value will be included in the analysis when 2 or more ALT values occur within the same visit window.

HBV DNA values (log₁₀ copies/mL)

- 1) Select the record closest to the nominal day (eg, Day 168 for analysis Week 24) for that visit.
- 2) If there are 2 visits equidistant from the nominal day, take the latest.
- 3) If there are multiple records on a selected day, take the geometric mean. If there are 2 values on the same day and it can be determined that the second one is a retest because there was a problem with the first test (for example, specimen hemolyzed), in these cases, the later value should be used.

All other laboratory parameters, DXA data, height, weight, and BMI

- 1) Select the record closest to the nominal day (eg, Day 168 for analysis Week 24) for that visit.
- 2) If there are 2 visits equidistant from the nominal day, take the latest.
- 3) For continuous variables, if there are multiple records on a selected day, take the arithmetic mean. For laboratory parameters, if there are 2 values on the same day and it can be determined that the second is a retest because there was a problem with the first test (for example, specimen hemolyzed), then the later value will be used. For categorical variables, if there are multiple records on a selected day, take the later value.

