Appendix 3. Table of Contents for Statistical Tables, Figures and Listings for the Final Analyses

Table Number	Title	Title	Analysis Set
1	Subject Enrollment		RAS
2	Subject Disposition		RAS
3	Demographics and Baseline Characteristics		SAS
4	Baseline Disease Characteristics		SAS
5	Concomitant Medications		SAS
6	Exposure to TDF		SAS
7	Adherence to TDF		
8.1	Number and Percentage of Subjects with HBV DNA < 400 copies/mL	by Week through Week 96 (M = E)	FAS
8.1.1	Number and Percentage of Subjects with HBV DNA < 400 copies/mL among Subjects with Normal ALT at Baseline	by Week through Week 96 (M = E)	FAS
8.1.2	Number and Percentage of Subjects with HBV DNA < 400 copies/mL among Subjects with Abnormal ALT at Baseline	by Week through Week 96 (M = E)	FAS
9	Log10 (HBV DNA) copies/mL and Change from Baseline	by Week through Week 96	FAS
10	HBsAg Change from Baseline	by Week through Week 96	FAS
11	Number and Percentage of Subjects with ALT Normal	by Week through Week 96 (M = E)	FAS
12	ALT (U/L) and Change from Baseline	by Week Through Treatment	FAS
13	Number and Percentage of Subjects with HBV DNA < 400 copies/mL and ALT Normal	by Week through Week 96 (M = E)	FAS
14	Number and Percentage of Subjects with HBeAg Loss/Seroconversion	by Week through Week 96 (M = E)	FAS who were HBeAg Positive at Baseline
15	Number and Percentage of Subjects with HBV DNA < 400 Copies/mL, ALT Normal, and HBeAg Seroconversion	by Week through Week 96 (M = E)	FAS who were HBeAg Positive at Baseline
16	Number and Percentage of Subjects with Normalized ALT	by Week through Week 96 (M = E)	FAS with Abnormal ALT at Baseline

Table Number	Title	Title	Analysis Set
17	Number and Percentage of Subjects with HBV DNA < 400 copies/mL and Normalized ALT	by Week through Week 96 (M = E)	FAS with Abnormal ALT at Baseline
18	Number and Percentage of Subjects with HBV DNA < 400 copies/mL, Normalized ALT, and HBeAg Seroconversion	by Week through Week 96 (M = E)	FAS who were HBeAg Positive with Abnormal ALT at Baseline
19.1	Treatment-Emergent Adverse Events Overall Summary	Bone or Renal	SAS
19.2.1	Treatment-Emergent Adverse Events by System Organ Class and Preferred Term	Grade 2, 3, or 4 Bone or Renal Adverse Events	SAS
19.2.3	Treatment-Emergent Adverse Events by System Organ Class and Preferred Term	Grade 3 or 4 Bone or Renal Adverse Events	SAS
19.3.1	Treatment-Emergent Adverse Events Related to TDF	Grade 2, 3, or 4 Bone or Renal Adverse Events	SAS

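### The trigger for anti-HBe testing differs between visits; on one natural reading, HBeAg seroconversion at Weeks 24, 48 and 72 is understated or cannot be determined

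*Protocol*

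**What the plan says.** Three rules for the same panel appear in the protocol.

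- **Weeks 24 and 72 (Section 6.4.3) and Week 48 (Section 6.4.4):** "HBV serology (HBeAg and HBsAg; anti-HBe and anti-HBs (if HBsAg negative".
- **Screening (6.2.1), Baseline (6.3.2) and Week 96/End of Treatment (6.4.6):** "HBV serology (HBeAg and HBsAg; anti-HBe and anti-HBs (if Ag negative".
- **Appendix 2 definition of HBV serology:** "HBeAg, HBsAg, anti-Hbe, anti-HBs", with no condition. The table marks it at Screening, Baseline and Weeks 24, 48, 72 and 96.

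The Synopsis gives the frequency as "HBV serology: every 24 weeks from Baseline to Week 96", also without a condition.

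SAP Appendix 3 lists Table 14, "Number and Percentage of Subjects with HBeAg Loss/Seroconversion", by week through Week 96 on a missing = excluded (M = E) basis, in subjects HBeAg positive at baseline. Tables 15 and 18 are composites that include HBeAg seroconversion, also by week and M = E.

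**The concern.** HBeAg seroconversion requires an anti-HBe result in a subject who has become HBeAg negative. Protocol Section 1.1 gives the usual order on treatment: "treatment can lead to HBeAg loss and, more rarely, anti-HBe seroconversion, with the goal of subsequent HBsAg loss and seroconversion to anti-HBs". The subject who matters is therefore typically HBeAg negative and still HBsAg positive. A trigger tied to HBsAg negativity misses that subject, while a trigger tied to either antigen, or no trigger, does not.

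At stake is whether a low seroconversion figure at Weeks 24 to 72 means that subjects did not convert or that they were not tested. As listed, the SAP tables would not let a reader tell the two apart. A rise between Week 72 and Week 96 could likewise come from a change in the test rule.

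**Working it through.** No sample-size or power figure is involved. The check compares the texts, with a little arithmetic.

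**1. What happens to a subject who is HBeAg negative and HBsAg positive**

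| Source | Visits | Bracket covers both antibodies | Bracket covers anti-HBs only |
|---|---|---|---|
| 6.2.1, 6.3.2, 6.4.6 | Screening, Baseline, Week 96 | anti-HBe tested (an antigen is negative) | anti-HBe tested |
| 6.4.3, 6.4.4 | Weeks 24, 48, 72 | anti-HBe **not** tested | anti-HBe tested |
| Appendix 2 | all of these | anti-HBe tested (no bracket) | anti-HBe tested |

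Only one cell loses information, but it covers 3 of the 4 scheduled post-baseline serology visits.

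**2. Which reading is natural.** The sentence and the position of the bracket are the same in all five sections. Where the trigger is the generic antigen, it follows both antigens and both antibodies, so it most naturally governs both antibodies. Only the trigger word changes in 6.4.3 and 6.4.4. Section 6 says that procedures are tabulated in Appendix 2 and described in the text, and gives neither precedence.

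**3. How many HBsAg-positive subjects could be affected.** The documents give no on-treatment HBsAg loss rate. Assuming 0% to 5%, the number of HBsAg-negative subjects among 30 is 30 × 0 = 0 to 30 × 0.05 = 1.5. On the strict reading, nearly all subjects would be ineligible for anti-HBe at Weeks 24 to 72.

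**4. Effect on the reported percentage, strict reading only (assumed counts).** Let N subjects be HBeAg positive at baseline, L lose HBeAg, C of those truly be anti-HBe positive, and none lose HBsAg. The true rate is C/N. The reported rate is 0/(N − L) if untested subjects are excluded, or 0/N if they count as not converted.

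| N / L / C (assumed) | True C/N | Untested excluded | Untested as failures |
|---|---|---|---|
| 15 / 2 / 1 | 6.7% | 0/13 | 0/15 |
| 20 / 4 / 3 | 15.0% | 0/16 | 0/20 |
| 25 / 5 / 4 | 16.0% | 0/20 | 0/25 |

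Exclusion removes exactly the subjects who lost HBeAg. SAP Section 3.7 has rules for borderline serology, but the SAP does not say how an HBeAg-negative subject without an anti-HBe result is classified.

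**5. How much Week 96 serology there can be.** SAP Sections 1.4 and 2.1 give 30 enrolled and two completing 96 weeks: 2/30 = 6.7%, so 28/30 = 93.3% did not complete. That is not the number with Week 96 serology. Protocol 6.4.6 also applies the Week 96 tests at an early discontinuation visit. The Week 96 serology window in SAP Table 3-3 runs from day 589 to day 756, that is 589/7 = 84.1 to 756/7 = 108.0 weeks.

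**The case against.** The strongest objection is that the bracket sits next to anti-HBs, the antibody that pairs with HBsAg, so it may cover that antibody alone. Anti-HBe would then be drawn at every serology visit and nothing would be lost. Appendix 2 supports this, as does the unconditional 24-week schedule. SAP Section 3.8.3 also expects the pair within a window: "In the event that 2 or more serology results (eg, HBeAg and anti-HBe or HBsAg and anti-HBs) occur within the same visit window". These points stand. They show that paired testing was probably intended, but they do not tell a site which text to follow.

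A reader might infer that anti-HBe was ordered only on HBsAg loss, so that seroconversion was almost undetectable before Week 96 and the tables must read about 0%. The documents do not support that as fact, because it holds on one of two readings. Even on that reading, a discontinuer tested under 6.4.6 is placed by study day. Day 350, for example, falls in the Week 48 window (days 253 to 420), so anti-HBe results can appear in earlier rows. Sections 6.4.2 to 6.4.5 carry their own discontinuation rules, and 6.4.2 and 6.4.5 list no serology. Which set each early discontinuer received is therefore unknown.

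A reader might also take 2 of 30 as the number who could contribute at Week 96. It counts 96-week completers only.

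The illustrative rates are assumptions. Section 1.1 calls anti-HBe seroconversion rarer than HBeAg loss, so scenarios in which 75% to 80% of those losing HBeAg convert may be generous. The remark about "with only a very small proportion of children clearing HBsAg and either exhibiting HBeAg loss or seroconversion" concerns initial infection and is not an on-treatment rate.

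Finally, the matter is peripheral. The primary outcome is bone safety, the efficacy endpoint is HBV DNA plus ALT, SAP Section 6.4 plans no secondary efficacy endpoints, and the final analysis is descriptive. This limits the importance. However, Protocol 8.1.3 lists immunological status as a secondary endpoint, and the three tables are planned.

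**Conclusion.** The inconsistency is real: three rules for one assay, with the restrictive wording at 3 of 4 scheduled post-baseline serology visits. The consequence is conditional. If the Week 24 to 72 bracket was applied to both antibodies, HBeAg seroconversion at those visits is understated or undeterminable in subjects who remain HBsAg positive, which affects Tables 14, 15 and 18. If it was applied to anti-HBs only, or Appendix 2 was followed, seroconversion is measurable. HBeAg loss is sound on either reading.

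The documents give no size for the bias, because they report neither the number HBeAg positive at baseline, nor the number who lost HBeAg, nor how sites read the text. This is a modest point about a descriptive secondary outcome, worth correcting because the correction costs almost nothing.

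**What to change.** **Protocol wording.** Reconcile Sections 6.2.1, 6.3.2, 6.4.3, 6.4.4 and 6.4.6 with Appendix 2. Either tie each antibody to its own antigen (anti-HBe if HBeAg negative; anti-HBs if HBsAg negative) or use the unconditional four-marker panel throughout. The early discontinuation visits that copy these lists follow automatically. The cost is a wording change and, under the first option, a reflex test on blood already drawn in HBeAg-negative subjects.

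**SAP, Tables 14, 15 and 18.** The last visit was in April 2018, so this is the part that can still affect the report.

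- Report HBeAg loss separately from seroconversion.
- At each week, show how many HBeAg-negative subjects had an anti-HBe result.
- State how HBeAg-negative subjects without an anti-HBe result are handled. M = E should not drop them silently, and they should not be counted silently as non-converters.

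The cost is about one extra row in each of three tables. Withholding a week's seroconversion figure unless every HBeAg-negative subject was tested is not needed; showing the number tested is enough.
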